#### 4.1.4. FIX Incremental Recovery

FIX incremental recovery will be measured up to 24 ( $\pm 1$ ) hours post-infusion of FIX protein products to assess time at maximum activity and percent recovery for exogenous FIX activity. The exogenous FIX activity levels will be determined by one-stage clotting assay. Participants are required to have at least 96 hours of washout for pd- or r-FIX or up to approximately 168 hours of washout for extended half-life rFIX prior to FIX incremental recovery test on Dosing Day (Day 0).

FIX incremental recovery assessments will be conducted by collecting blood samples at various time-points up to 24 ( $\pm 1$ ) hours from the start of FIX protein product infusion. Blood samples on Day 0 will be collected pre-infusion, 10 ( $\pm 2$ ) minutes, 1 hour  $\pm 10$  minutes, 3 hours  $\pm 10$  minutes, 6 hours  $\pm 10$  minutes, and 24 ( $\pm 1$ ) hours from the start-of-infusion of FIX protein product.

Samples for thrombin generation assessments will also be collected on Day 0 at pre-infusion and 10 ( $\pm 2$ ) minutes from the start-of-infusion of FIX protein infusion and evaluated by an

CCI performed at the central laboratory. For participants at selected sites depending on the testing capabilities, additional samples for global hemostasis may also be collected at pre-infusion and 10 ( $\pm$ 2) minutes from the start-of-infusion of FIX protein infusion and evaluated by the whole blood TEG and/or rotational thromboelastogram (ROTEM) locally.

#### 4.1.5. Immunomodulation Optimization (ONLY for Participants Who Develop Hepatitis Transaminitis)

Based on observation and experience from earlier clinical studies of liver-directed AAV gene transfer, including the SJ-UCL trial, earlier clinical studies sponsored by Spark Therapeutics', who was also the initial Sponsor of this study, and the Baxter trial (NCT#01687608), participants may develop an apparent immune response to the vector capsid participants, as evidenced by a transient rise in transaminases (AST and/or ALT) and an increase in AAV capsid-specific T cells in the peripheral blood. Immunomodulation will be instituted for these participants in an effort to limit the immunologic response in the liver and maintain endogenous FIX expression.

A tapering course of oral corticosteroids will be the first consideration for suppression of apparent immune hepatitis. The rationale for this approach is that corticosteroids are effective in severe autoimmune hepatitis, a disease in which hepatocytes are attacked by epitope-specific cytotoxic T lymphocyte (CTL). The mechanism for this immune reactivity is not clear, but viruses may be causal.

Based on guidelines published by the American Association for the Study of Liver Diseases (AASLD) and in the absence of alternative etiology, and from the study data of the SJ-UCL group, treatment for vector-induced hepatitis would be instituted if:

1. In the absence of alternative causes, a transaminase value is approximately 1.5-fold above baseline (Day 0) OR is successively increasing during follow-up (at the Investigator's discretion, they may choose to wait for a repeat transaminase value which remains elevated, or is further increased, or they may choose to initiate treatment); or
2. Vector-derived FIX:C activity levels decline without evidence of inhibitor, corticosteroids may be added at the discretion of the Investigator.

Oral corticosteroids (such as prednisolone/prednisone) will be used per the AASLD guidelines, with modification allowed by the Investigator and agreed by the medical monitor based on response to laboratory parameters and/or participant tolerance of the regimen:

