	
transaminases (alanine aminotransferase [ALT] and/or aspartate transaminase [AST]) elevation of approximately 1.5-fold or successively increasing during follow-up above baseline (or vector-derived FIX:C activity levels decline without evidence of FIX inhibitor, accompanied by rising interferon [IFN] enzyme-linked immunospot assays [ELISPOTs] on peripheral blood mononuclear cells [PBMCs]) after PF-06838435 infusion, treatment with corticosteroids will be instituted. Alternative immunosuppressive therapies will be considered if the initial corticosteroid treatments are not successful.
 
For any individual who reaches >150% vector-derived FIX:C activity levels after the infusion of PF-06838435, laboratory parameters of thrombotic potential will be assessed.

Secondary	

The secondary objective is to characterize the kinetics of PF-06838435.

	

Vector-derived FIX:C activity levels:

Peak

Steady-state

FIX antigen levels

CCI
 	

	
CCI
 
[REDACTED]

--	------------------------------

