**3. OBJECTIVES, ESTIMANDS AND ENDPOINTS**

Objectives	Endpoints
Primary	

 
The primary objective is to evaluate the safety and tolerability of a single IV infusion of PF-06838435 in hemophilia B participants ≥18 years of age with ≤2 IU/dL [≤2 %] endogenous factor IX [FIX].
 
	
Clinically significant changes from baseline in the following:
 
 
Physical examination
 
Vital signs
 
Laboratory values
 
Incidence of drug-related adverse events (including inhibitor development)
 
FIX incremental recovery (time at maximum activity [Tmax] and percent recovery for FIX activity)
 
Immune response against AAV capsid protein
 
Immune response against hFIX transgene
 
 
For those individuals who develop hepatic transaminases (ALT and/or AST) elevation of approximately 1.5-fold or successively increasing during follow-up above baseline (or vector-derived FIX:C activity levels decline without evidence of FIX inhibitor, accompanied by rising IFN ELISPOTs on PBMCs) after PF-06838435 infusion, treatment with corticosteroids will be instituted. Alternative immunosuppressive

	
therapies will be considered if the initial corticosteroid treatments are not successful.
 
For any individual who reaches >150% vector-derived FIX:C activity levels after the infusion of PF-06838435, laboratory parameters of thrombotic potential will be assessed.

Secondary	

• The secondary objective is to characterize the kinetics of PF-06838435.

	

• Vector-derived FIX:C activity levels:

• Peak

• Steady-state

• FIX antigen levels

CCI
 	

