If immune hepatitis develops in any participant, following investigational product administration and if 2 or more participants are non-responsive to immunomodulatory regimens, or if the value of the transaminases continue to rise, consideration of more intensive immunomodulatory regimens will be entertained per recommendation from the independent Data DMC. Regimen recommendations will require agreement from the DMC, Sponsor Medical Monitor, and the Investigator.

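### For a FIX:C decline without inhibitor, the Synopsis and Section 3 make corticosteroids mandatory when ELISPOTs rise, while Section 4.1.5 makes them optional with no ELISPOT condition

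*Protocol*

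**What the plan says.** The Synopsis (Objectives, Estimands and Endpoints) and Protocol Section 3 carry the same rule in the endpoints column. Besides a transaminase trigger, Section 3 names this one: "vector-derived FIX:C activity levels decline without evidence of FIX inhibitor, accompanied by rising IFN ELISPOTs on PBMCs". The instruction attached to both triggers is that, "after PF-06838435 infusion, treatment with corticosteroids will be instituted".

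Protocol Section 4.1.5 states the triggers again as a two-item list. The lead-in is "treatment for vector-induced hepatitis would be instituted if". Item 1 is the transaminase trigger. It adds that investigators have a choice: "they may choose to wait for a repeat transaminase value which remains elevated", or they may start treatment. Item 2 is the FIX:C trigger: "Vector-derived FIX:C activity levels decline without evidence of inhibitor, corticosteroids may be added at the discretion of the Investigator". The section heading limits all of this to participants who develop transaminitis. The section gives preserving the participant's own FIX expression as one aim of immunomodulation.

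SAP Section 7.1 plans an additional listing of corticosteroid and other immunosuppressive use. It defines that listing by transaminase elevation only, as does the title of Listing 16.2.5.3.

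**The concern.** The two statements differ in both the condition and the force of the instruction, and neither refers to the other. Which participants receive corticosteroids for a falling FIX:C could then depend on which section a site works from.

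This matters for the analysis because the treatment acts on the measured quantity. Appendix 6 of the protocol (Section 10.6) says the immune reaction can show as a liver-test rise, a FIX fall or both, and that it has responded to corticosteroids. Steady-state FIX:C is a secondary endpoint, and it also feeds the decision counts in Section 4.1.3.1. One expansion scenario there turns on whether a capsid-related decline was well managed by corticosteroids, which presupposes a settled rule for giving them. The estimand in Section 9.1.1 deals with intercurrent FIX product infusions and does not mention corticosteroid use. Different treatment practice would therefore pass into the summaries without being identified.

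**Working it through.** No figure in the plan can be reproduced for this point. The check sets the passages side by side.

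**Step 1. Condition and force in each place**

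| Place | FIX:C decline without inhibitor | ELISPOT condition | Force |
|---|---|---|---|
| Synopsis and Section 3 | yes | yes, must be rising | mandatory |
| Section 4.1.5, lead-in | covers both items | none | worded as an instruction |
| Section 4.1.5, item 2 | yes | none | investigator's discretion |
| Section 4.1.5, heading | excluded unless transaminitis is present | none | not stated |
| SAP 7.1 corticosteroid listing | not covered | none | not applicable |

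In Section 3 the ELISPOT condition and the instruction belong to one sentence: "accompanied by rising IFN ELISPOTs on PBMCs) after PF-06838435 infusion, treatment with corticosteroids will be instituted". ELISPOT is not absent from Section 4.1.5 in general. Table 1, note b, uses it in the taper. Its absence from item 2 is therefore a difference in the trigger, and is not explained by the section leaving that assay aside.

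**Step 2. Apply both rules to each kind of participant (no inhibitor throughout)**

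| Participant | Synopsis and Section 3 | Section 4.1.5 | Result |
|---|---|---|---|
| (a) FIX:C falls, ELISPOT rising, no transaminase rise | treat | may treat | direct conflict |
| (b) FIX:C falls, ELISPOT not rising, no transaminase rise | no trigger | may treat | different criteria |
| (c) Transaminases about 1.5-fold above baseline or successively increasing | treat | treat, or wait for a repeat value | lesser difference in discretion |

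Read literally, the heading of 4.1.5 removes (a) and (b) from that section altogether, so item 2 would never apply on its own.

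**Step 3. How sensitive the decision counts are**

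The thresholds in Section 4.1.3.1 are at least 3 participants at 40% or more (no escalation), fewer than 3 between 3% and 40% (escalation), 3 of 5 above 5% (first expansion) and 6 of 10 above 5% (further expansion). One participant is 1/5 = 20% of the first expansion group and 1/10 = 10% of the second. If exactly 3 of 5 stand above 5% and one of them falls below it, the count becomes 3 − 1 = 2 and the criterion fails. This shows how small the counts are. It is not a prediction that it will happen.

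**Step 4. What cannot be calculated**

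The documents do not say how many participants would fall in (a) or (b), or how much FIX:C is lost when a decline is left untreated. The shift in mean steady-state FIX:C therefore cannot be estimated.

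**Step 5. Whether the data would show it**

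A participant treated for a FIX:C decline alone would be outside the SAP's corticosteroid listing. He would still appear in the general medication listing (16.2.5.2), but SAP 7.1 does not provide for showing which trigger led to treatment.

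**The case against.** The best answer is that the passages can be read together: mandatory when ELISPOT rises, discretionary otherwise. That settles participant (b). It does not settle (a), because item 2 leaves the decision to the investigator without excepting a rising ELISPOT, and no text states the combined rule.

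It can also be said that Section 4.1.5 is the operative text, since the Schedule of Activities points there, and that Section 3 only summarises. That may describe practice, but Section 3 is worded as an instruction and nothing gives 4.1.5 precedence. The flexibility that 4.1.5 grants elsewhere concerns the regimen and its course.

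Several limits stand. Group (a) may be small or empty. The study is single-arm and descriptive, with no hypothesis test. Corticosteroid use is recorded as concomitant medication, and events caused by immunomodulatory drugs are recorded as connected to those drugs. The Schema notes that no escalation had occurred before Amendment 7, so the public text does not show how many dose decisions remain open.

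A reader might also infer a conflict over second-line treatment. The Synopsis says "Alternative immunosuppressive therapies will be considered if the initial corticosteroid treatments are not successful", while Section 4.1.5 mentions more intensive regimens "if 2 or more participants are non-responsive to immunomodulatory regimens", or if transaminases go on rising. The documents do not support this reading. Section 4.1.5 and its Table 2 already give an individual participant a combined intravenous and oral step, and the later, DMC-guided step can be read as a further tier.

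**Conclusion.** The point holds as an internal inconsistency. One kind of participant (a) is under contradictory instructions, a second (b) has a trigger in one place and none in the other, and Section 4.1.5 disagrees with its own lead-in and heading. The option to wait for a repeat transaminase value is a lesser difference, since both texts call for treatment in that case.

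The effect on steady-state FIX:C and on the escalation and expansion counts is plausible but has no size that the documents can supply. It rests on two assumptions taken from the protocol: that corticosteroids help to preserve FIX expression, and that some participants show a FIX:C fall without a transaminase rise.

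A reader might go further and infer that the Section 3 wording would put many participants on corticosteroids through chance runs of rising transaminases, whereas 4.1.5 would filter them out. The documents do not support that. Both sections use the unquantified criterion of successive increase, 4.1.5 also allows treatment at once, and any rate would depend on how many readings count as successive, which neither defines. Nor do the documents support a claim that FIX:C is biased in a known direction.

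**What to change.** Reconcile the Synopsis, Section 3 and Section 4.1.5. Put one statement of the triggers in 4.1.5, saying for each whether ELISPOT is required and whether action is mandatory or discretionary, including the repeat-value option. Have the Synopsis and Section 3 refer to it without restating it. Correct the 4.1.5 heading so that it matches the participants covered. The sponsor and DMC choose the rule; this review takes no position on it.

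Add a CRF field for the trigger that led to treatment. Extend the listing in SAP 7.1, and the title of Listing 16.2.5.3, to participants treated for a FIX:C decline.

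The cost is protocol wording in three places, one CRF field and one SAP listing definition. No added visit, sample or participant is needed.

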**Table 1. Recommended Initial Regimen for Oral Corticosteroids**

Schedule	Prednisolone/Prednisone (mg/day)
Week 1	~100 - 60
Week 2	60 a
Week 3	40

**Table 1. Recommended Initial Regimen for Oral Corticosteroids**

Schedule	Prednisolone/Prednisone (mg/day)
Week 4	30
Week 5	30
Week 6	20 b
Week 7	15
Week 8	10

a. Please see paragraph below.

b. Maintain at 20 mg/day until transaminases (and ELISPOT) return to baseline, then reduce by 5 mg/day until 10 mg/day are achieved then reduce by 2.5 mg/week up to 5 mg daily.

Approximately 100-60 mg/PO (orally) QD (once a day) of oral corticosteroids for the first week is recommended as the starting dose unless the Investigator believes a different regimen should be implemented based on the participant's medical history. Per the judgment of the Investigator, 60 mg/PO QDa can be extended to another week if the participant has no adverse effect. The subsequent prednisolone/prednisone taper should not be started until the ALT and/or AST have begun to decline or have returned to approximately baseline (pre-administration) levels. See [Table 1](#) above.

The following schedule of combined oral corticosteroids and IV corticosteroids (methylprednisolone) is recommended if there is no evidence of resolution of transaminase elevation while on oral corticosteroids treatment alone.

**Table 2. Recommended Regimen for Combination Intravenous and Oral Corticosteroids**

Schedule	Prednisolone/Prednisone (mg/day)	Methylprednisolone (g/day)
Day 1-3	n/a	1
Day 4-7	20	n/a
Week 2	60	n/a
Week 3	60	n/a
Week 4	40	n/a
Week 5	30	n/a
Week 6	30	n/a
Week 7	20	n/a
Week 8	10	n/a
Week 9	5	n/a

There is extensive experience with corticosteroids and immunosuppressive regimens in hemophilia: first, as a maneuver to eradicate antibodies to factor VIII or IX, clinically termed inhibitors and second, in the setting of liver transplantation due to the high prevalence of hepatitis C among adults with hemophilia. Many individuals with hemophilia have been maintained on standard liver transplant immunosuppression regimens for years.

Corticosteroids have been used to treat people with asthma, idiopathic thrombocytopenic purpura, and other medical conditions for years. For participants with severe hemophilia B, the benefit of long-term expression of a modest level of clotting factor far outweighs the risk of a course of immunomodulatory drugs.

The Investigator will have flexibility in implementing the immunomodulatory regimen since the exact regimen and course will depend on clinical circumstances. The long-term side effects of the immunomodulatory drugs to be considered in this study are well characterized. Participants who develop immune hepatitis will be monitored closely to minimize the risk of the side effects. To utilize the lowest effective dose and to shorten the duration of the immunosuppressive therapies, tapering of the regimen will start as soon as there is evidence of resolution of hepatic transaminases elevation and disappearance from the peripheral blood of capsid-specific T cells. While on immunomodulatory regimens, participants will also be monitored for side effects, including opportunistic infections. Antibiotics or other medications to minimize the risk of opportunistic infection may be prescribed at the discretion of the Investigator. All events related to the use of immunomodulatory drugs (eg, hyperglycemia, weight gain, infections) will be recorded as adverse events connected to their use.

If immune hepatitis develops in any participant, following investigational product administration and if 2 or more participants are non-responsive to immunomodulatory regimens, or if the value of the transaminases continue to rise, consideration of more intensive immunomodulatory regimens will be entertained per recommendation from the independent Data DMC. Regimen recommendations will require agreement from the DMC, Sponsor Medical Monitor, and the Investigator.

#### **4.1.6. Thrombotic Potential Assessments (ONLY for Participants Who Reach Vector-derived FIX:C Activity Levels >150% after the infusion of PF-06838435)**

Based on non-clinical studies in NHPs and the and the now closed Baxter study using hFIX-Padua, it is not predicted that vector-derived FIX:C activity levels >150% of normal will be achieved in this study. However, thrombin-antithrombin levels (TAT) as thrombotic potential will be measured if vector-derived FIX:C activity levels >150% of normal are achieved in any participant during the study. Blood samples for TAT on Day 0 (prior to FIX protein product infusion) will be used to establish baseline value.

#### **4.1.7. Duration of Study Participation**

The study will consist of the following phases:

1. Screening period (up to 6 [ $\pm$ 2] weeks);
2. Dosing day (Day 0);
3. Safety observation period (52 [ $\pm$ 2] weeks post-infusion of PF-06838435).

The total duration of the study is approximately 58 weeks (including up to 6 weeks of screening).

#### **4.1.7.1. Screening Period**

Potential participants will undergo the screening assessments described in the Schedule of Activities up to 6 ( $\pm 2$ ) weeks prior to the infusion of PF-06838435 once the consent process is completed at the vector-administration center. If the screening result of FIX:C activity level is  $>2\%$  due to recent infusion of factor IX protein product, then the severity of hemophilia B may be confirmed by documented historical evidence from a certified laboratory demonstrating the FIX:C activity level  $\leq 2\%$  or from a documented genotype known to produce a clinically severe phenotype of hemophilia B. If FIX:C activity is not  $\leq 2\%$  at screening or documented historical evidence is not available and genotype are not known, sample(s) will be drawn for analysis at Screening. Genotype is not a criterion for inclusion or exclusion. However, a documented genotype known to produce a clinically severe phenotype of hemophilia B is required if the participant is otherwise unable to demonstrate severity. Once the eligibility is verified, participants are required to undergo a washout of FIX protein products for at least 96 hours (4 days) prior to the Dosing Day (Day 0) to establish baseline value of FIX:C and FIX inhibitor. The screening period may be extended up to 2 weeks for participants who have a bleeding event requiring FIX protein product infusion within 96 hours prior to Day 0 (Dosing Day). If screening is prolonged greater than 8 weeks, then the FIX inhibitor, anti-AAV-Spark100 capsid antibody, biochemistry, hematology, vital signs, and physical examination screening assessments must be repeated to ensure continued eligibility. The reason for prolongation of screening should be clearly documented.

Screening assessments would also be done to verify participant eligibility are described in [Section 8.10.1](#).

#### **4.1.7.2. Dosing Day**

Assessments and procedures to be performed on Dosing Day (Day 0) are described in the Schedule of Activities. Participants will receive a bolus infusion of FIX protein product in about 10 minutes for FIX incremental recovery ([Section 6.1.1](#)) followed by a single IV infusion of PF-06838435 at the vector-administration center. The complete dose of PF-06838435 will be infused via infusion pump over a period of approximately 60 minutes under medical supervision. Vital signs will be taken at various time-points up to approximately 24 hours from the start of infusion (see Schedule of Activities).

Blood samples for FIX incremental recovery will be collected pre-infusion of the FIX protein product, 10 ( $\pm 2$ ) minutes [end-of-infusion], 1 hour  $\pm 10$  minutes, 3 hours  $\pm 10$  minutes, 6 hours  $\pm 10$  minutes, and 24 ( $\pm 1$ ) hours from the start-of-infusion. Samples for thrombin generation assessments will also be collected pre-infusion and 10 ( $\pm 2$ ) minutes from the start-of-infusion of FIX protein infusion and evaluated by an CCI performed at the central laboratory. For participants at selected sites, depending on the testing capabilities, additional samples for global hemostasis such as whole blood TEG and/or ROTEM may also be collected pre-infusion and 10 ( $\pm 2$ ) minutes from the start-of-infusion of FIX protein infusion and evaluated locally.

